9.3 Definition of Populations

Our population includes patients 18-65 years old who have tested positive with COVID-19 in the prior 10 days, and/or have symptom development in the prior 10 days (for symptomatic participants). Inclusion and exclusion criteria (described elsewhere) will be met. We are not treating patients for their COVID-19 infection.

9.4 Outcomes

All oral rinse products are commercially available, low risk products. Therefore, adverse outcomes are anticipated to be extremely rare, and will be reviewed weekly by the study team/committee. Any adverse event or deviation will be documented in our CDART database system. All significant adverse events (SAEs) will be reported appropriately to the IRB.

The qRT-PCR and viral infectivity assays for our primary outcome will be documented in excel spreadsheets generated by the qRT-PCR and viral infectivity assay quantification devices, available weeks to months after sample collection when the experiments are conducted. Samples will be run in large batches. The survey results will also yield excel spreadsheets of data, available shortly after data collection.

The outcomes do not include patient treatment response, and therefore the outcomes will not be reviewed and adjudicated by an outside committee. The study personnel will constitute their own committee that meets weekly, and they will review and evaluate the data once these experiments are conducted. The committee will not be masked to the participant's group assignment; the statistician will conduct analyses and then the committee will evaluate the data to reach scientific conclusions on which mouth rinse is more effective.

9.4.1 Primary Outcome

The primary objective of this study is to determine the efficacy of antiseptic mouthwashes on reducing SARS-CoV-2 cellular infectivity in COVID+ patient saliva. *We hypothesize that COVID-19+ patients will have a >95% reduction in SARS-CoV-2 viral infectivity following a 60 second oral rinse with an antiseptic mouth rinse and that this reduction will persist for at least 30 minutes.* This primary objective will focus on quantifying SARS-CoV-2 viral infectivity and RNA level using an *in vitro* infectivity assay and quantitative real time PCR. This objective provides urgently needed data to guide healthcare workers on the proper use of specific commercially available mouthwashes capable of reducing SARS-CoV-2 viral infectivity and potentially limiting COVID-19+ transmission.

Outcome assessments will be conducted weeks to months after the study visit, when qRT-PCR and viral infectivity assays are conducted in the COVID core and the [name] lab.

9.4.2 Secondary Outcomes

There is no secondary objective.

9.4.3 Tertiary Outcomes

The tertiary objective is to determine the acceptability of using antiseptic mouthwashes on reducing SARS-CoV-2 cellular infectivity by patients in settings including healthcare contexts. *We hypothesize that patients will welcome the use of commercially available antiseptic mouth rinses into clinical practice.* All patients will be surveyed on the taste, appearance, sensation, and acceptability of using the mouth rinse in healthcare settings. Understanding acceptability of a mouth rinse protocol is critical to implementation and therefore the ability to reduce COVID-19 transmission risk in clinical settings.

Survey results will be evaluated using bivariate, descriptive statistics and non-parametric methods as appropriate for the question type. Outcome assessments will be conducted weeks to months after the study visit, when statistical analyses are conducted.

9.5 Data Analyses All data analyzed will be deidentified.

qRT-PCR: Data will be presented as mean standard deviation for normally distributed data and as median [Interquartile range] for non-normally distributed data. P values will be reported as two tailed. Between group comparisons will be performed using a Students t test or Mann-Whitney test. Normality will be assessed using the Kolmogorov-Smirnov test, and logistic regression will be performed with robust standard errors. Methods adapted from Bullard *et al* 2020.

Viral infectivity: The viral infectivity analysis will compare infectivity levels between mouth rinse types and across the time course for calculation of the reduction factor (RF). The RF will be calculated as the difference in the quotient of the infection titre before ('control titration') and after the mouth rinse ('remaining virus'). Therefore, the log10 titre and its (double) standard deviation (SD) were calculated as well as the variance of the RF.

Survey results will be evaluated using bivariate, descriptive statistics and non-parametric methods as appropriate for the question type.

Power Calculation: Based on our similar viral load studies evaluating mouth rinse efficacy against SARS-COV-2 and other enveloped viruses, we used power calculations to estimate effect size and determine sample size as a function of length of mouth rinse time course.¹² The sample size is justified by a paired t-test on outcomes between time points. With simultaneous comparisons, the sample size n=43 for each mouth rinse can detect the effect size in Cohen's d =0.8, which is between medium and large, under 80% power and 0.016 type-I error rate by Bonferroni correction.¹² To account for 14% of patients having no virus in their saliva, we plan to enroll 55 participants per arm. Analyses will compare viral RNA level (qRT-PCR) and viral infectivity levels between mouth rinse types and across the time course. ANCOVA models will be utilized to look at changes in viral load and infectivity logarithmically before and after treatment.

10. DATA COLLECTION AND QUALITY ASSURANCE

10.1 Data Collection Forms

Consented patients' data (including screening questions, demographics, and the survey on mouth rinse acceptability) will be collected using the CDART dental toolkit program, which stores data on a secure UNC maintained server and meets federal guidelines for clinical study data acquisition. The CDART electronic forms and database will serve as our CRFs and source data. IRB approved study personnel will ask participants the questions and will enter responses into this encrypted, password protected database. Data will be collected in this program using participant's study ID and no other personal health identifiers (PHI). A separate linkage file for participants ID and name will be set-up and maintained by the study coordinators and will be securely stored on UNC servers. This linkage file will be kept confidential, and not shared with anyone outside of the study coordinators. Clinical data will only be transmitted among the research team using the school of dentistry secure research servers. Demographic data will be transmitted among the research team through access to the secure CDART research database system, stored on secure UNC servers, which study personnel will access only through encrypted computers via secure user accounts.

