[name], Study Coordinator, [name], [contact], [contact]

[name], Study Coordinator, [name], 1 [contact], [contact]

[name], Study Coordinator, [name], [contact], [contact]

[name], Research Assistant, GO Health Clinic, [name], [contact], [contact]

[name], Research Assistant, GO Health Clinic, [name], [contact], [contact]

[name], GO Health Clinic Manager [name], [contact], [contact]

[name], Statistician, [name], [contact], [contact]

[name]. Statistician (survey data), Howard W. Odum Institute for Research in Social Science, [name], 1 [contact], [contact]

PRÉCIS

Study Title

Antiviral Efficacy of Therapeutic Antiseptic Mouth Rinses for Inactivation of COVID SARS-2 Virus

Objectives

The primary objective is to quantify the impact of antiseptic mouthwashes on salivary infectivity in COVID-19+ patients. The secondary objective is to determine patients' acceptance of using antiseptic mouthwashes in healthcare settings.

Design and Outcomes

Randomized, double-blind prospective trial to test the efficacy and acceptability of two therapeutic, antiseptic mouth rinses to inactivate SARS-CoV-2 virus in saliva of COVID-19 positive patients aged 18-65 years old. Both mouth rinses are commercially available and will be used according to on-label instructions. Patients will be randomized to a mouth rinse and will be asked to give a saliva sample immediately before and after a one-minute mouthwash. Saliva samples will be collected from patients at 15-minute intervals thereafter up to an hour (15, 30, 45 and 60 minutes). The samples will be stored and used for RT-PCR detection of viral SARS-CoV-2 RNA and viral infectivity assays. Patients will also complete a short-survey on the taste and experience of using the mouthwash. This study involves one, 75-90 minute visit.

Interventions and Duration

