1.3 Tertiary Objectives

The tertiary objective is to determine the acceptability of using antiseptic mouthwashes on reducing SARS-CoV-2 cellular infectivity by patients in various settings including healthcare contexts. *We hypothesize that patients will welcome the use of commercially available antiseptic mouth rinses into clinical practice.* All patients enrolled will be surveyed on the taste, appearance, sensation, and acceptability of using the mouth rinse in different settings. Understanding acceptability of a mouth rinse protocol is critical to implementation and therefore the ability to reduce COVID-19 transmission risk in clinical settings.

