6.2 Description of Evaluations

Subjects are required to be onsite for a 70-90 minute, single visit appointment. After consenting and confirmation of meeting inclusion/exclusion criteria, subjects will be asked to rinse with an unlabeled/blinded antiviral mouth rinse for 60 seconds and provide 5 mL of saliva prior to the rinse and 2 mL of saliva immediately post-rinse, 15 minutes post-rinse, 30 minutes post-rinse, 45 minutes post-rinse, and 60 minutes post-rinse. Subjects will also be asked questions as part of a short survey about the rinsing experience and their willingness to rinse in different situations.

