6.2.2 Enrollment, Baseline, and/or Randomization

Enrollment

Outpatient subjects will be recruited from patients seen in the UNC Respiratory Diagnostic Clinic (RDC), UNC testing sites or UNC hospital who have tested positive for COVID-19. Subjects will be contacted for recruitment by phone and (if unreachable by phone) by secure email by study personnel; patients will have the study rationale and risks explained and will be provided time to ask questions and consider participation. If patients are interested in participating, a single appointment will be scheduled for them at the Adams School of Dentistry Go Health Clinical research core in the associated clinical research isolation area. Consent documentation will be signed in person and in private in the Clinical Research Core. A list of COVID+ subjects will be provided by the RDC clinic and EPIC, accessible via secure UNC servers or secure UNC email to our research team's clinical coordinator, and this list will include names and contact details (PHI). This list is updated daily and provided to approved research sites, including ours.

Baseline Assessments

Study personnel confirm enrollment qualifying criteria and perform a COVID rapid antigen test and pregnancy test on applicable individuals. Otherwise, there are no baseline assessments required as this study only requires a 70-90 minute single visit appointment.

Randomization

Our statistician will create a block randomization tool which will be provided to the unblinded study staff ([name]) to perform the randomization. In the instance that [name] is unavailable, [name] or [name] will perform randomization and set-up the rinses. The participant's group assignment will be communicated to the blinded clinical staff. All patients will be consented and then complete our screening questions for inclusion and exclusion to confirm eligibility prior to being assigned to the randomization schedule.

The researcher in charge of collecting the salivary samples will be blinded to the mouthwash solution, as they will be given a pre-aliquoted mouth rinse in an unlabeled storage tube to provide to the patient for the rinse.

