6.2.5 Completion/Final Evaluation

This study requires only one 70-90 minute, single visit appointment. After consenting and randomization, subjects will be asked to rinse with an unlabeled/blinded antiviral mouth rinse for 60 seconds and provide 5 mL of saliva prior to the rinse and 2 mL of saliva immediately post-rinse, 15 minutes post-rinse, 30 minutes post-rinse, 45 minutes post-

rinse, and 60 minutes post-rinse. Subjects will also be asked to complete a short survey about the rinsing experience.

Subjects may withdraw from the trial at any time at their own request, or they may be withdrawn at any time at the discretion of the Investigator or Sponsor for safety, behavioral or administrative reasons.

The Investigator may discontinue a subject if, in the opinion of the Investigator, the subject is no longer a suitable candidate for the study. Possible reasons for the discontinuation of a subject are including but not limited to: adverse event, protocol deviation, missed appointment, subject no longer meets the eligibility criteria.

Patients may be removed from the study due to an allergic reaction to a mouth rinse or due to failure or inability to comply with study procedures.

If a patient suffers from severe xerostomia/dry mouth, such that s/he cannot produce the baseline salivary sample volume or the immediate, 15 minute and 30 minute post-rinse saliva volumes, s/he will be removed from the study with a parking voucher, but without a gift card and will be replaced. If a patient suffers from dry mouth, such that s/he cannot produce salivary sample volumes needed for later time points (45 minutes or 60 minutes post-rinse) but s/he produced sufficient baseline, immediate, 15 minute and 30 minute post-rinse samples, s/he will still be compensated with a gift card and parking vouchers, and will remain in the study. Missing or deficient salivary samples will be noted in CDART. Severe xerostomia is an exclusion criteria during screening, yet we anticipate that some individuals may not know that they have severe xerostomia until they are participating in the study visit and then need to discontinue due to reduced salivary flow, as described.

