10.2 Data Management

An Excel key will be created by the study coordinators with study ID (random alphanumeric code) to identify patients, saved in a secure folder on a UNC SOD server. This linkage file will be stored separately from data and destroyed at the close of the study and will never be shared beyond the study coordinators.

All data collected from participants and results from sample analysis will be coded with unique numerical identifiers and stored in the UNC CDART clinical research database and on a secure UNC-CH server. Only trained, IRB-approved study personnel will enter and access data in the secure CDART research database.

Consented patients' data (including screening questions, demographics, and the survey on mouth rinse acceptability) will be collected using the CDART dental toolkit program, which stores data on a secure UNC maintained server and meets federal guidelines for clinical study data acquisition. Only HIPAA and human subjects trained, IRB-approved study personnel will collect, enter and manage patient data; study coordinators will serve in this capacity.

Data will be collected in the CDART research database using participant's study ID and no other PHI identifiers, on approved, carefully designed digital forms within CDART. CDART forms will include questions with drop downs, radio button multiple choice and text field entry, depending on the question type. There will be separate digital forms for inclusion/exclusion screening questions (before sample collection begins), demographic

questions, and questions regarding mouth rinse experience (taste, color, sensation) and willingness to use a mouth rinse in various settings (e.g. dentist or doctor appointments). A separate linkage file, securely stored on UNC servers, will be utilized to associate the random alphanumeric study ID with patient identifier, so samples and CDART data will not be associated with patient identifiers.

Data will only be transmitted among the research team using the SOD secure research server. Demographic data will be transmitted among the research team through access to the secure CDART research database system, stored on secure UNC servers, which study personnel will access only through encrypted computers via secure user account.

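### The acceptability survey is staff-asked and staff-entered with no safeguard, so the absolute acceptance level is exposed to social-desirability bias (a minor point)

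*Combined protocol and SAP*

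**What the plan says.** Section 10.1 defines the data it covers as "including screening questions, demographics, and the survey on mouth rinse acceptability) will be collected using the CDART dental toolkit program", and then gives one mode for all of it: "IRB approved study personnel will ask participants the questions and will enter responses into this encrypted, password protected database". Section 10.2 is consistent with this: "Only HIPAA and human subjects trained, IRB-approved study personnel will collect, enter and manage patient data". It names the study coordinators for that task and restricts entry and access in CDART to study personnel. Section 6.2 also fits: "Subjects will also be asked questions as part of a short survey about the rinsing experience".

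Three other places use looser wording. The Précis (Design and Outcomes) says "Patients will also complete a short-survey on the taste and experience of using the mouthwash". The Précis (Interventions and Duration) and section 6.2.5 say "Subjects will also be asked to complete a short survey about the rinsing experience". None of them gives a mode.

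Sections 3 and 5.1 place the survey in the ten-minute break after the first post-rinse sample, while the participant is still in the visit. The hypothesis in section 1.3 is "We hypothesize that patients will welcome the use of commercially available antiseptic mouth rinses into clinical practice". Section 9.1 words the related hypothesis as good tolerance by a majority. The survey analysis in sections 9.1, 9.4.3 and 9.5 is descriptive or bivariate, with no survey test, power or sample size.

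**The concern.** As written, a participant rates the rinse and states willingness to use it aloud, to a member of the team running the study, who then records the answer. That is a recognised setting for social-desirability bias, meaning answers more favourable than the respondent would give in private. No section describes private completion, anonymity towards the interviewer, or any other protection.

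Both hypotheses concern an absolute level of acceptance. Any upward shift would therefore move the result in the hypothesised direction, and a descriptive analysis could neither detect nor remove it. Sections 1.3 and 9.4.3 treat acceptability as critical to implementation, and the survey is given once, so a mode effect could not be repaired afterwards.

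**Working it through.** **Step 1: which mode is specified?** The places that bear on it, side by side:

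| Place | What it gives |
|---|---|
| 10.1 | Staff ask and staff enter; the acceptability survey is explicitly included |
| 10.2 | Staff collect and enter; only study personnel enter and access CDART data |
| 6.2 | Subjects are asked the survey questions |
| 3 and 5.1 | Participants answer during the break; neutral on mode |
| Précis (two places) and 6.2.5 | Participants complete a survey; no mode |

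The verb in the last row does not settle the mode. Section 6.2.2 uses it for the eligibility questions, "All patients will be consented and then complete our screening questions for inclusion and exclusion", and section 9.2 says that study personnel ask those same questions. The specified mode is therefore face to face, and nothing in the text contradicts it.

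**Step 2: is there a figure of the plan's to reproduce?** No. The documents give no sample size, power or alpha for the survey, and no size for a mode effect. The shifts below are assumptions.

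**Step 3: inputs.**
- Active-rinse respondents: 2 × 84 = 168 (Précis; table in section 3). Sections 2.2, 9.1, 9.2 and 9.5 instead give 55 per arm, so 2 × 55 = 110 is also run.
- Cut-off: more than half. This is borrowed from the majority wording in section 9.1, because the hypothesis in section 1.3 has no threshold.
- Assumed true acceptance: 48% and 60%. Assumed shift: 0, 5 or 10 points.

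**Step 4: chance of an observed majority.** P(X > n/2), with X binomial (n, true proportion + shift):

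| True acceptance | Shift | n = 168 | n = 110 |
|---|---|---|---|
| 48% | 0 | 0.275 | 0.303 |
| 48% | 5 points | 0.759 | 0.704 |
| 48% | 10 points | 0.978 | 0.945 |
| 60% | 0 | 0.995 | 0.979 |

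Near 50%, an assumed shift of 5 points changes the likely conclusion. At a true 60%, a majority is almost certain without any shift. Which enrolment figure applies makes little difference.

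**Step 5: sampling error.** The 95% half-width at 48% with n = 168 is 1.96 × √(0.48 × 0.52 / 168) = 0.0755, or 7.6 points. An assumed 5-point shift is somewhat smaller than this and a 10-point shift is larger.

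**Step 6: does a larger sample help?** At a proportion of 50% the half-width falls from 10.7 points (n = 84) to 6.2 (n = 252), while a systematic shift stays where it is. With true acceptance 50% and an assumed 10-point shift, the nominal 95% interval contains the truth 51% of the time at n = 84 and 11% at n = 252.

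**Step 7: between arms.** If each arm has true proportion p and a common shift b, the observed difference is (p₁ + b) − (p₂ + b) = p₁ − p₂. A similar shift in every arm drops out of comparisons between rinses, including those with water. It remains in each arm's own level.

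**The case against.** The strongest case against the point is that staff administration is a legitimate way to run a short survey of infectious participants, some of whom need a translator. The outcome is tertiary in sections 1.3 and 9.4.3 (secondary in the Précis and section 9.1) and is analysed descriptively. All arms are surveyed alike by staff who are meant to be blinded, so comparisons between rinses are largely protected. The illustration in step 4 also depends on placing true acceptance just below the cut-off. All of this stands, and it limits the point to the absolute level and to a minor rank.

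Four stronger readings are tempting, and the documents support none of them:
- **That the protocol contradicts itself**, with some sections having patients fill in the survey alone. No section says so, and the wording relied on is also used for questions that staff ask.
- **That the result is biased.** The documents show exposure to a risk. They give neither its direction nor its size.
- **That the gift card adds pressure from the interviewer.** Sections 3 and 5.1 do not say who hands it over. Sections 6.2.5 and 8 withhold it for insufficient early saliva, and nowhere is it tied to survey answers.
- **That poor ratings are softened most for the least pleasant rinse**, hiding differences between products. This is conceivable, since taste may reveal the rinse to the participant, but nothing in the documents supports it.

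**Conclusion.** The point holds in a limited form. The plan specifies face-to-face collection with staff entry for the acceptability survey and describes no safeguard, so the absolute acceptance result is exposed to social-desirability bias of unknown size. If such a bias exists, more participants would not reduce it.

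Its practical effect depends on two quantities that the documents do not give: the size of the shift and the true level of acceptance. It would alter a majority conclusion only if true acceptance is close to 50%; well above that, it would inflate the reported percentage without changing the conclusion. Comparisons between arms are largely unaffected if the shift is similar in each. This is a minor, optional-level improvement to a non-primary, descriptive outcome, and the primary virological outcome is not touched.

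**What to change.** In section 10.1, separate the forms by mode. Keep staff-asked entry for the screening questions. Have participants complete the rinse-experience and willingness form privately, in English or Spanish, by one of two routes:
- on a tablet, with a one-line amendment to the section 10.2 rule that restricts CDART entry and access to study personnel, after confirming that CDART allows participant-facing entry, which the documents do not state; or
- on paper, later transcribed by staff, which leaves that rule intact.

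Where a participant needs the form read aloud, record that the mode was assisted. Use the same mode in all three arms and state it consistently in sections 3, 6.2, 10.1 and 10.2. If staff administration is kept, say so once and name social-desirability bias as a limitation when acceptance levels are reported.

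The cost is protocol wording plus either tablet disinfection between participants or transcription of a short form, and probably a few skipped items. No extra staff or participants are needed.
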